SD	standard deviation
SGLT	sodium glucose co-transporter
SGOT	serum glutamic oxaloacetic transaminase
SGPT	serum glutamic pyruvic transaminase
SOM	Site Operations Manual
SUSAR	Suspected Unexpected Serious Adverse Reactions
T2DM	type 2 diabetes mellitus
TBL	total bilirubin
UGE	urinary glucose excretion
ULN	upper limit of normal
ULOQ	upper limit of quantification
WBC	white blood cell(s)
WHO	World Health Organization

[figure not shown]
Pharmacokinetic definitions and symbols

Ae0-t	Amount of drug (or defined metabolite) excreted into the urine from time zero to time 't' where t is a defined time point after administration [mass units or % of dose]
AUCinf	The area under the plasma concentration-time curve from time zero to infinity [mass x time / volume]
AUClast	The area under the plasma concentration-time curve from time zero to the time of the last quantifiable concentration [mass x time / volume]
AUCtau	The area under the plasma concentration-time curve from time zero to the end of the dosing interval tau [mass x time / volume]
CL/F	The apparent systemic (or total body) clearance from plasma (or serum or blood) following extravascular administration [volume / time]
CLr	The renal clearance from plasma [volume / time]
Cmax	The observed maximum plasma concentration following drug administration [mass / volume]
F	Bioavailability of a compound.
T1/2	The terminal elimination half-life [time]
Tmax	The time to reach the maximum concentration after drug administration [time]
Vz/F	The apparent volume of distribution during the terminal elimination phase following extravascular administration [volume]

Glossary of terms

Assessment	A procedure used to generate data required by the study
Cohort	A specific group of subjects fulfilling certain criteria
Dosage	Dose of the study treatment given to the subject in a time unit (e.g. 100 mg once a day, 75 mg twice a day)
Enrollment	Point/time of subject entry into the study at which informed consent must be obtained (i.e. prior to starting any of the procedures described in the protocol)
Epoch	Interval of time in the planned conduct of a study. An epoch is associated with a purpose (e.g. screening, treatment, follow-up) which applies across all arms of a study.
Healthy volunteer	A person with no known significant health problems who volunteers to be a study participant
Investigational drug	The study drug whose properties are being tested in the study; this definition is consistent with US CFR 21 Section 312.3 and Directive 2001/20/EC and is synonymous with “investigational new drug” or “test substance”
Patient	An individual with the condition of interest
Period	A minor subdivision of the study timeline; divides phases into smaller functional segments such as screening, baseline, titration, washout, etc.
Premature subject withdrawal	Point/time when the subject exits from the study prior to the planned completion of all study drug administration and assessments; at this time all study drug administration is discontinued and no further assessments are planned.
Screen Failure	A subject who is screened but is not treated
Stage	A major subdivision of the study timeline; begins and ends with major study milestones such as enrollment, completion of treatment, etc.
Study completion	Point/time at which the subject came in for a final evaluation visit or when study drug was discontinued whichever is later.
Study drug discontinuation	Point/time when subject permanently stops taking study drug for any reason; may or may not also be the point/time of premature subject withdrawal.
Study drug/treatment	Any drug (or combination of drugs) administered to the subject as part of the required study procedures; includes investigational drug, active drug run-ins or background therapy.
Study treatment	Any drug administered to the study participants as part of the required study procedures; includes investigational drug (s), control(s) or non-investigational medicinal product(s)

[figure not shown]
Study treatment discontinuation	When the subject permanently stops taking study treatment prior to the defined study treatment completion date
Subject	A trial participant (can be a healthy volunteer or a patient)
Subject number	A unique number assigned to each subject upon signing the informed consent. This number is the definitive, unique identifier for the subject and should be used to identify the subject throughout the study for all data collected, sample labels, etc.
Treatment number	A unique identifier assigned in non-randomized studies to each dosed subject, corresponding to a specific treatment arm
Variable	A measured value or assessed response that is determined in specific assessments and used in data analysis to evaluate the drug being tested in the study
Withdrawal of consent (WoC)	Withdrawal of consent from the study is defined as when a subject does not want to participate in the study any longer, and does not want any further visits or assessments, and does not want any further study related contact, and does not allow analysis of already obtained biologic material

Protocol synopsis

Protocol number	CLIK066B2202
Title	An open-label, parallel-group study to assess the effect of LIK066 on urinary glucose excretion, pharmacokinetics, safety and tolerability following multiple dose administration in patients with decreased renal function compared to subjects with normal renal function
Brief title	Study of pharmacodynamics, pharmacokinetics, safety and tolerability of LIK066 in patients with decreased renal function
Sponsor and Clinical Trial Phase	Novartis Phase II
Intervention type	Investigational Drug
Study type	Interventional
Purpose and rationale	The purpose of this study is: 1) to determine whether LIK066 displays a similar effect on the urinary glucose excretion in patients with varying degrees of reduced renal function as those with normal renal function, and 2) to assess the pharmacokinetics of LIK066 in patients with varying degrees of renal impairment as compared to those with normal renal function; to support development of LIK066 in patients with renal impairment
Primary Objectives	
 To assess the effect of a 7-day treatment with LIK066 on 24-hour urinary glucose excretion in subjects with decreased renal function compared to those with normal renal function. To assess the pharmacokinetics of LIK066 on Day 1 and Day 7 in subjects with decreased renal function compared to those with normal renal function.
Secondary Objective	
 To assess the safety and tolerability of a 7-day treatment with LIK066 in subjects with decreased renal function compared to those with normal renal function.
Study design	
An open-label, multiple-dose, parallel-group study in patients with varying degrees of decreased renal function (mild, moderate and severe renal impairment) and subjects with normal renal function. Each subject will participate in a screening period of up to 28 days, one baseline period, one treatment period of 7 days (including domicile and outpatient visits), a follow-up period, and an end-of-study evaluation approximately 96 hours after the last drug administration.
 
Eligible subjects will be admitted to the study site at Baseline (Day -2). Meal contents including carbohydrates and salt will be standardized from Day -2 to the morning of Day 2, and then from Day 5 to Day 8, [REDACTED]. LIK066 treatment will be administered once daily after an overnight fast, before breakfast from Day 1 to Day 7. Subjects can be domiciled during the study per the investigator discretion. The study assessments will include 24-hour urine collection and blood collections for pharmacokinetic, pharmacodynamics, safety [REDACTED].
 
Study completion evaluations will be performed after the last pharmacokinetic assessment is completed (Day 11), or in the case of early termination, prior to discharge from the study site.

Population	
Ten (10) subjects each with mild (eGFR 60-89 ml/min/1.73 m²), Grade A moderate (eGFR 46-59 ml/min/1.73 m²), Grade B moderate (eGFR 30-45 ml/min/1.73 m²), and normal renal function (eGFR ≥90 ml/min/1.73 m²); and up to 10 patients with severe renal impairment (eGFR ≤29 ml/min/1.73 m², not on dialysis) will be enrolled in this study.
 
Patients with varying degrees of decreased renal function will be enrolled first; subjects with normal renal function will be enrolled after approximately 50% of the patients with decreased renal function (at least two in each group of patients with moderate renal impairment, and at least one patient in the group of patients with severe renal impairment) have been enrolled. The 10 subjects with normal renal function will be matched to 10 of the enrolled patients with decreased renal function by age, weight, and, if possible, diabetic status.

Key Inclusion criteria	
All individuals:
 
• Male and female subjects age 18 to 78 years, inclusive, with BMI ≤ 50 kg/m² and with controlled health condition as determined by past medical history, physical examination, electrocardiogram, and laboratory tests at screening.• For patients with Type 2 diabetes, HbAc1 < 10% at screening. If treated with antidiabetic medications (other than prohibited medications), patients must be on a stable dose for approximately 6 weeks prior to starting the study treatment and maintain the dose until the end of the study. 
Patients with decreased renal function:
 
• Patients must have stable renal disease without evidence of active progression at screening (for the purpose of this study stable renal disease will be defined as no significant change of eGFR for 12 weeks, per the discretion of the investigator upon reviewing the medical history or previous lab assessments).
• Mild renal impairment: eGFR from 60 to 89 ml/min/1.73 m²• Grade A moderate renal impairment: eGFR from 46 to 59 ml/min/1.73 m²• Grade B moderate renal impairment: eGFR from 30 to 45 ml/min/1.73 m²• Severe renal impairment: eGFR of ≤ 29 ml/min/1.73 m², not on dialysis 
Subjects with normal renal function:
 
• Normal renal function reflected by an eGFR of ≥90 ml/min/1.73m².• Subjects will be matched to 10 of the enrolled patients with decreased renal function by age (approximately ± 10 years), weight (approximately ± 20%), and, if possible, diabetic status.

Key Exclusion criteria	All individuals: 
• Pregnant or nursing (lactating) women. Women of child-bearing potential, unless they are using basic methods of contraception during the study.• Patients with type 1 diabetes, or history of acute diabetic complications such as ketoacidosis or hyperosmolar state (coma) within the 6 months prior to screening.• Evidence of urinary obstruction or difficulty in voiding at screening• Symptomatic genital or urinary tract infection (UTI) in the 4 weeks prior to screening or the presence of active UTI at screening• Any finding during screening assessments (physical examination, vital signs, ECG or clinical lab assessments), surgical or medical condition which might significantly alter the absorption, distribution, metabolism, or excretion of drugs, or which may jeopardize the subject, per the investigator's judgment, in case of participation in the study.• Clinically significant GI disorder related to malabsorption or GI surgery that may affect drug or glucose absorption (e.g. swallowing disorder, severe GI motility disorder, chronic diarrhea, glucose/galactose/lactose intolerance)• Use of prohibited medications Patients with decreased renal function: 
• Hemoglobin levels <8.0 g/dl at screening Subjects with normal renal function: 
• Hemoglobin levels <12.0 g/dl for males, or <11.0 g/dl for females at screening
Study treatment	The investigational drug, LIK066 tablets will be prepared by Novartis. This is an open label nonrandomized study. All subjects will receive LIK066 50 mg once daily before breakfast for 7 days.
Efficacy/PD assessments	
• Urinary glucose excretion
Key safety assessments	
• Physical examination• Body temperature• Hematology• Blood chemistry• Urinalysis• Blood pressure• Pulse rate• ECG evaluation• Adverse events and serious adverse events
	

Data analysis	The primary analyses will assess the effect of reduced renal function on 24-hour urinary glucose excretion (UGE24) and on the PK of LIK066. The change from baseline in UGE24 will be analyzed using an analysis of covariance model with diabetic status, renal impaired group, day, and all associated interactions (where possible) as fixed factors and age, baseline body weight, and baseline fasting plasma glucose as covariates. Each of the log-transformed PK parameters will be analyzed using the same model but without the baseline covariates.
Key words	Decreased renal function. Urinary glucose excretion. Pharmacokinetics

1 Introduction

[figure not shown]
[figure not shown]
Obesity has become a major global health problem that contributes causally to and exacerbates many serious co-morbidities including hypertension, dyslipidemia, and importantly type 2 diabetes (T2DM). In contrast to the numerous medicines that are available to treat these obesity-related diseases, relatively few agents are available for the treatment of obesity itself that are effective, safe or scalable to the size of the affected population (Morgen and Sorensen 2014). A novel mechanism to lower body weight is via inhibition of the sodium glucose co-transporters 1 and 2 (SGLTs) resulting in inhibition of the glucose absorption in the gut and reabsorption in the kidney (Chao and Henry 2010). In healthy subjects, virtually all of the filtered glucose is reabsorbed into the circulation and no glucose is detected in the urine. SGLT2 located in the segments 1 and 2 of the proximal tubule contributes to ~90% of reabsorption of the filtered glucose (Abdul-Ghani et al 2015). SGLT1 is located in the more distal part of the proximal tubule, segment 3, and contributes to the remaining ~10% of filtered glucose. However, when SGLT2 is inhibited with empagliflozin (a SGLT2 inhibitor), SGLT1 compensates for the reabsorption of filtered glucose and SGLT1 is capable of reabsorbing >40% of filtered glucose load in a mouse model (Abdul-Ghani et al 2015). In addition to expression in the kidney, SGLT1 is also expressed in the small intestine, where it is required for glucose and galactose absorption. Inhibition of enteric SGLT1 results in glucose and galactose malabsorption (Turk et al 1991), which results in calorie wasting and other potential endocrine-based weight loss mechanisms.

LIK066 is a potent dual inhibitor of SGLT1/2, which has been studied in healthy subjects, patients with T2DM, and obese patients with elevated BMI. LIK066 is generally safe and well tolerated in the clinical studies being completed to date. LIK066 has a favorable pharmacokinetic profile (T_{1/2} of 10-16 hours), which allows once daily dosing. LIK066 at 150 mg daily dose (as qd, bid or tid) results in a significant weight loss in obese patients; ~ 6% decrease in body weight was demonstrated after 12 week treatment.

All selective SGLT2 inhibitors being approved in the clinical practice are either not recommended or contraindicated in patients with moderate or severe renal impairment (either eGFR<60; or eGFR<45 mL/min) primarily due to lack of efficacy and certain safety concerns. Dual inhibition of SGLT1 and SGLT2 leads to further caloric wasting of glucose attributed to reduced absorption of glucose from the intestine and enhanced inhibition of glucose reabsorption from the kidneys, which is a major mechanistic differentiation from a selective SGLT2 inhibitor. This study is designed to assess the potential efficacy of LIK066 in patients with moderate or severe chronic kidney disease using 24-hour urinary glucose excretion (UGE₂₄) as the primary surrogate endpoint. The design of this study will also evaluate the PK of LIK066 in patients with reduced renal function. Safety and tolerability of LIK066 at 50 mg qd for 7 days will also be assessed in this patient population with reduced renal function.

1.1 Background

[figure not shown]
[figure not shown]
[figure not shown]
The most relevant data for the present study are summarized in the sections below. For detailed information, please refer to the Investigator's Brochure.

[figure not shown]

[Redacted content]

[Redacted content]

[Redacted content]

1.4 Study purpose

The purpose of this study is: 1) to determine whether LIK066 displays a similar effect on the urinary glucose excretion in patients with varying degrees of reduced renal function as those with normal renal function, and 2) to assess the pharmacokinetics of LIK066 in patients with varying degrees of renal impairment as compared to those with normal renal function; to support development of LIK066 in patients with kidney disease.

2 Study objectives and endpoints

[figure not shown]
2.1 Primary objectives

Primary objectives	Endpoints related to primary objectives

To assess the effect of a 7-day treatment with LIK066 on 24-hour urinary glucose excretion (UGE) in subjects with decreased renal function compared to those with normal renal function	
24-hour urinary glucose excretion on Day 7

To assess the pharmacokinetics of LIK066 on Day 1 and Day 7 in subjects with decreased renal function compared to those with normal renal function	
C_{max}, T_{max}, AUC_{tau}, AUC_{last}, AUC_{inf}, T_{1/2}, CL/F, V_z/F, CL_r

2.2 Secondary objective

Secondary objective	Endpoints related to secondary objective

To assess the safety and tolerability of a 7-day treatment with LIK066 in subjects with decreased renal function compared to those with normal renal function	
Adverse events

3 Investigational plan

[figure not shown]
3.1 Study design

This study employs an open-label, multiple-dose, parallel-group design in patients with varying degrees of decreased renal function (mild, moderate and severe renal impairment) and subjects with normal renal function. The most common cause of chronic kidney disease is diabetes, which accounts for roughly 50% of all cases. Approximately 50% of the patients enrolled in each group of the mild, moderate and severe renal impairment are expected to be patients with T2DM.

Each subject will participate in a screening period of up to 28 days, one baseline period, one treatment period of 7 days (including domicile and outpatient visits), a follow-up period, and an end-of-study evaluation approximately 96 hours after the last drug administration.

Ten (10) subjects each with mild (eGFR 60-89 ml/min/1.73 m²), Grade A moderate (eGFR 46-59 ml/min/1.73 m²), Grade B moderate (eGFR 30-45 ml/min/1.73 m²), and normal renal function (eGFR ≥90 ml/min/1.73 m²); and up to 10 patients with severe renal impairment (eGFR ≤29 ml/min/1.73 m², not on dialysis) will be enrolled.

Figure 3-1 Study design

Patients with varying degrees of decreased renal function will be enrolled first; subjects with normal renal function will be enrolled after approximately 50% of the patients with decreased renal function (at least two in each group of patients with moderate renal impairment, and at least one patient in the group of patients with severe renal impairment) have been enrolled. Because body weight and age are covariates in the estimation of eGFR formula, the 10 subjects with normal renal function will be matched to 10 of the enrolled patients with

decreased renal function by age (approximately ± 10 years), weight (approximately $\pm 20\%$), and, if possible, diabetic status. The 10 patients with decreased renal function on whom the matching will be based will be selected so as to cover as broad age range as possible. The enrolled patients will be ranked by age and selected, beginning with the youngest and ending with the oldest, in an increment that yields 10 total patients. Efforts will be made to match the diabetic status, where possible, to ensure representation of both diabetic and non-diabetic populations in the group of subjects with normal renal function.

The renal function (eGFR) will be assessed based on the MDRD equation ([Levey et al 2006](#)) during the screening visit. The MDRD equation (Serum creatinine levels in mg/dl) to be used is as follows:

$$\text{eGFR} = 175 \times \text{Serum Creatinine}^{-1.154} \times \text{Age}^{-0.203} \times [1.212 \text{ if Black}] \times [0.742 \text{ if Female}]$$

Additional details about the eGFR equations and the standardized creatinine assays will be provided in the SOM.

Each subject will attend Screening visit(s) when the inclusion/exclusion criteria will be assessed. Eligible subjects will be admitted to the study site at Baseline (Day -2), where eligibility for enrollment into the study will be confirmed as needed. All baseline safety evaluation results must be available and reviewed prior to dosing when screening is performed more than 7 days prior to dosing. Each subject will receive once daily LIK066 at 50 mg dose for 7 days. Meal contents including carbohydrates and salt will be standardized from Day -2 to the morning of Day 2, and then from Day 5 to Day 8, [REDACTED]

[REDACTED] Detailed information on meal recommendation is provided in the SOM. Baseline twenty-four hour urine samples will be collected. Study participants must be fasted for approximately 10 hours before Day 1 dosing of LIK066. Standardized breakfast will be provided immediately after the administration of LIK066 in the morning.

Following the first dose on Day 1, subjects will remain domiciled for at least 24 hours for collection of urine and blood samples for urinary glucose excretion, pharmacokinetic, pharmacodynamic and safety assessments. Subjects will either remain domiciled (mandatory for subjects with severe renal impairment) or return in the morning to the study site every day (Day 3 to Day 5) to receive their medication after approximately 10-hour fasting overnight, per the investigator discretion as described in the SOM. A standardized breakfast will be served immediately after administration of LIK066 every day. Subjects will be domiciled from Day 5 and will be fasted for approximately 10 hours before the final dose on the morning of Day 7 at the site. Subjects will remain domiciled up to Day 8 to complete 24-hour collection of urine and blood for urinary glucose excretion, pharmacokinetic, pharmacodynamic and safety assessments after the final dose. Blood and urine samples for pharmacokinetic assessments will be taken on Days 9, 10 and 11 (up to 96 hours post the final dose). Study completion evaluations will be performed after the last pharmacokinetic assessment is completed (Day 11), or in the case of early termination, prior to discharge from the study site.

Safety assessments will include physical examinations, ECGs, vital signs, standard clinical laboratory evaluations (blood chemistry, urinalysis, hematology), and adverse event and serious adverse event monitoring. See the assessment schedule for further details.

[REDACTED]

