3.2 Rationale of study design

[figure not shown]
[figure not shown]
The design of this study addresses the primary objective of assessing the effects of LIK066 on urinary glucose excretion and the pharmacokinetics of LIK066 in subjects with reduced renal function as compared to those with normal renal function. The 24-hour urinary glucose excretion (UGE24) is zero in healthy subjects and ~10 g in patients with T2DM in the absence of a SGLT inhibitor such as LIK066. The UGE24 is ~100 g when LIK066 is given to patients with T2DM, therefore, the diabetic status is expected to have little impact on the assessment of UGE24. In addition, the assessment of UGE24 will be based on the changes corrected by baseline UGE24. The matching of subjects with normal renal function to a subset of the subjects with reduced renal function will be done to minimize bias in the comparison due to confounding factors of age, body weight, and diabetic status. An open-label design without a placebo comparator is appropriate as the primary endpoints, 24-hour urinary glucose excretion and pharmacokinetics, are objective parameters.

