4.1.3 Subjects with normal renal function

9. Except for the medical conditions allowed in the inclusion/exclusion criteria (e.g. diabetes or hypertension), no other significant medical conditions at screening or baseline as determined by medical history and physical examination.
10. Normal renal function reflected by an eGFR of ≥ 90 ml/min/1.73m².
11. Vital signs (after 3 minutes resting measured in the supine position). The Investigator should be guided by the following ranges:
 - oral body temperature between 35.0-37.2°C
 - systolic blood pressure, 100-150 mm Hg
 - diastolic blood pressure, 60-100 mm Hg
 - pulse rate, 45-100 bpm

Blood pressure and pulse will be taken again in a standing position. After 3 minutes standing, there shall be no more than a 20 mm Hg drop in systolic or 10 mm Hg drop in diastolic blood pressure associated with clinical manifestation of no symptomatic postural hypotension.

12. Subjects will be matched to 10 of the enrolled patients with decreased renal function by age (approximately ± 10 years), weight (approximately $\pm 20\%$), and, if possible, diabetic status.

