5.3 Statistical model, assumptions and hypotheses

The natural logarithm of each PK parameter will be analyzed using a MMRM model with diabetic status, renal function group, day, and all associated interactions (where possible) as fixed factors and age as covariate. An unstructured covariance matrix will be used.

For each parameter, the least-square geometric mean will be estimated for each diabetic status by renal function by day combination. In addition, the geometric mean ratio of each renal impaired group to the group with normal renal function and the corresponding two-sided 90%

confidence interval and p-value for the ratio will be extracted for each diabetic status by day combination.

Statistical analysis may be performed to compare the free fraction (f_u) across the renal function groups. If statistically significant difference exists in f_u across renal function groups, the same analysis (as planned for total parameters) will also be performed to compare the $AUC_{0-\infty,u}$ and $C_{max,u}$ between renal function groups. [REDACTED]

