6.1.3 Statistical model, assumptions and hypotheses

The primary PD analysis will assess the effect of reduced renal function on UGE24.

The change from baseline in UGE24 will be analyzed using a MMRM with diabetic status, renal function group, day, and all associated interactions (where possible) as fixed factors and age, baseline body weight, and baseline fasting plasma glucose as covariates. Baseline fasting plasma glucose and baseline body weight will be the measurements on Day 1 0-hour. An unstructured covariance matrix will be used.

The least-square mean change from baseline will be estimated for each diabetic status by renal function by day combination. In addition, the mean difference between each renal impaired group and the group with normal renal function (or other least severe group with data) and the corresponding two-sided 90% confidence interval and p-value for the difference will be extracted for each diabetic status by day combination.

Additionally, the change from baseline in UGE24 will be analyzed for the overall group, using a MMRM with diabetic status, renal function group, day, and interaction terms of renal function*day and diabetic*day as fixed factors and age, baseline body weight and baseline fasting plasma glucose as covariates. An unstructured covariate matrix will be used.

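### The eGFR-formula reason given for matching on body weight is wrong; separately, sex is neither matched nor modelled, although ten non-randomised controls are the reference for every contrast with normal

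*Protocol*

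**What the plan says.** Protocol 3.1 gives the reason for matching: "Because body weight and age are covariates in the estimation of eGFR formula". SAP 1.4 repeats it. Protocol 3.1 then names the equation: "The MDRD equation (Serum creatinine levels in mg/dl) to be used is as follows". Its terms are serum creatinine, age, a factor of 1.212 for Black race and a factor of 0.742 for female sex. SAP 1.4 prints no equation.

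Protocol 3.2 gives a second reason for matching, which does not use the formula: "to minimize bias in the comparison due to confounding factors of age, body weight, and diabetic status".

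The matching rule is criterion 12 in Protocol 4.1.3: "Subjects will be matched to 10 of the enrolled patients with decreased renal function by age" (about ±10 years), weight (about ±20%) and, where possible, diabetic status. The ten patients to be matched are picked by age rank (Protocol 3.1). Both sexes are eligible (Protocol 4.1.1).

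The UGE24 model in SAP 6.1.3 has diabetic status, renal group and day with their interactions, and "age, baseline body weight, and baseline fasting plasma glucose as covariates". Protocol 11.4.2 has the same list. For PK, Protocol 11.4.2 drops the baseline covariates, and SAP 5.3 takes diabetic status, renal group, day and their interactions "as fixed factors and age as covariate". No model in either document includes sex.

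**The concern.** There are two separate points.

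The first is a factual error in the stated rationale. A reader who checks the sentence against the equation printed after it finds that weight is not there.

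The second is a gap in the design and analysis. Renal groups are not randomised, and ten controls are the reference for every comparison with normal renal function. The contrasts are extracted within each diabetic status by day combination, so the controls of a given diabetic status serve all contrasts of that status. If their sex mix differs from that of the impaired groups, and sex affects glucose excretion or exposure at the fixed 50 mg dose, those contrasts all move in the same direction. The confidence intervals describe sampling error under the fitted model and would not show such a shift. For PK, neither sex nor weight is in the model.

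**Working it through.** **1. Stated reason against the equation.**

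| Factor | In the printed MDRD equation | Matched | UGE24 model | PK model (SAP) |
|---|---|---|---|---|
| Age | yes | yes | yes | yes |
| Body weight | no | yes | yes | no |
| Sex | yes (0.742 if female) | no | no | no |
| Black race | yes (1.212) | no | no | no |
| Diabetic status | no | if possible | yes | yes |

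The reason in 3.1 holds for age and fails for weight. The reason in 3.2 covers age, weight and diabetic status without the formula.

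**2. The plan's own precision figures** (Protocol 11.7; 8 completers per group, two-sided 90% CI). Both reproduce with a t quantile on 7 degrees of freedom.
- UGE24: SE = 24 × √(2/8) = 12 g. The plan's half-width of 22.7 g is recovered as 22.73 g.
- Cmax: CV 22% gives a log-scale SD of √ln(1 + 0.22²) = 0.2174. The limits are 0.814 and 1.229 times the observed ratio, matching the plan's 0.81 and 1.23.

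**3. How large could a shift be?** The documents give no sex effect on UGE24 or exposure and no expected sex mix. Every effect and imbalance below is an assumption.
- PK: let r be the ratio of exposure in women to that in men, and d the difference in the share of women between two groups. The geometric mean ratio is multiplied by r^d. With r from 1.1 to 1.3 and d from 0.2 to 0.4, the range is 1.1^0.2 = 1.019 to 1.3^0.4 = 1.111, about 2% to 11%.
- UGE24: a sex effect of 5 to 20 g and the same imbalances give 5 × 0.2 = 1 g to 20 × 0.4 = 8 g, against the 22.7 g half-width.

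**4. How likely are such imbalances?** Assume 30% to 50% women in each group, with sex left to chance.
- Two groups of 10 differ by 3 or more women with probability 0.22 to 0.26, and by 4 or more with probability 0.08 to 0.12.
- Protocol 3.1 expects about half of each impaired group to have T2DM. If the controls split likewise (an assumption), a cell behind a reported contrast holds about 5 subjects, and one subject is 20 points. Two cells of 5 differ by 2 or more women (40 points) with probability 0.30 to 0.34.

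An imbalance of 40 points would thus be unusual between whole groups but not rare between cells. The intervals for those smaller cells are also wider than the figures in step 2.

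**5. Cost of a sex term.** The UGE24 model has 5 × 2 = 10 group-by-status cells and 3 covariates, so 13 between-subject terms. A sex main effect makes 14, with at most 50 subjects.

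**The case against.** The strongest reply is that correcting the sentence changes no subject, match or analysis, because Protocol 3.2 justifies weight matching on its own. That stands. A reader might infer that the whole matching scheme rests on a false premise. The documents do not support this: the reason is right for age, and weight keeps its confounding rationale.

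A second reply is that a place in an eGFR equation does not make sex a confounder. That also stands. At age 60 and creatinine 1.0 mg/dL, the equation gives 175 × 60^(-0.203) = 76.2 for a non-Black man (mild) and 76.2 × 0.742 = 56.6 for a non-Black woman (Grade A moderate). It is tempting to read this as sex driving group assignment and so as evidence of bias. It shows only the equation applying its sex factor at equal creatinine. It says nothing about the sex mix of the groups or about any effect on the endpoints.

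Third, the plan is not wholly without protection. Weight matching within about ±20%, and the weight covariate for UGE24, may absorb part of a sex effect that acts through body size. Demographics are summarised by renal function (Protocol 11.2, SAP 7.2), so a whole-group imbalance would be visible, although those summaries are not split by diabetic status. Seeing an imbalance also does not adjust for it.

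Fourth, formula membership would equally call for matching on race. It would, so the case for sex here does not use that criterion. It rests on the small, shared, non-randomised reference group. Race is likewise unmatched and unmodelled, and a sentence explaining its omission would help.

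**Conclusion.** Two facts are certain from the text. The reason given for weight in Protocol 3.1 and SAP 1.4 contradicts the printed equation, and sex appears in neither the matching nor any primary model. The first is a wording error with no effect on the results.

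The second is an unguarded factor whose effect is unknown. The PK shift of about 2-11% and the UGE24 shift of 1-8 g rest entirely on assumed sex effects and imbalances. The PK shift lies inside the plan's 0.81-1.23 range, and the UGE24 shift is below its 22.7 g half-width. A reader might infer that the primary estimates are biased by these amounts, but nothing in the documents shows that. What is supported is a cheap improvement to a design in which one control group serves every contrast with normal.

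**What to change.** - **Rationale, Protocol 3.1 and SAP 1.4 only:** replace the eGFR-formula reason with the confounding reason of Protocol 3.2. The synopsis and criterion 12 do not contain the faulty sentence.
- **Matching lists (synopsis, Protocol 3.1, criterion 12, SAP 1.4):** add sex, to be matched where possible, with the same standing as diabetic status.
- **SAP 5.3 and 6.1.3.1:** add one supportive run of each primary model with sex as a covariate. The primary models and the sample size stay as they are.

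The cost is wording in two documents, one extra model per endpoint and possibly slightly slower control recruitment, which the where-possible standing limits. No new data are needed, since the MDRD equation already requires each subject's sex. If controls are already enrolled, the corrected rationale and the supportive runs can still be made.
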